**Table 3. Potential Drug Abuse AE PTs from Clinical Review**

PTs
Thought broadcasting
Thought insertion
Thought withdrawal
Time perception altered
Tobacco abuse
Tobacco interaction
Tobacco withdrawal symptoms
Trance
Transient global amnesia
Transient psychosis
Unresponsive to stimuli
Verbigeration
Violence-related symptom
Visual perseveration
Withdrawal syndrome

**Table 4. Euphoria-related AE PTs from Clinical Review**

PTs
Euphoric mood
Feeling abnormal
Feeling drunk
Feeling of relaxation
Hallucination
Hallucination, auditory
Hallucination, gustatory
Hallucination, olfactory
Hallucination, synaesthetic
Hallucination, tactile
Hallucination, visual
Hallucinations, mixed
Inappropriate affect
Thinking abnormal

### Appendix 3.2. Local Irritation AEs

**Table 5. PTs in “Application and Instillation Site Reactions” HLT from Clinical Review**

PTs
Administration site anaesthesia
Administration site discolouration
Administration site discomfort
Administration site dryness
Administration site dysaesthesia
Administration site erythema
Administration site exfoliation
Administration site haemorrhage
Administration site inflammation
Administration site irritation
Administration site necrosis
Administration site oedema
Administration site pain
Administration site paraesthesia
Administration site reaction
Administration site swelling
Administration site ulcer
Administration site urticaria

**Table 6. PTs in “Upper Respiratory Tract Signs and Symptoms” HLT from Clinical Review**

PTs
Catarrh
Choking sensation
Dry throat
Increased upper airway secretion
Increased viscosity of upper respiratory secretion
Laryngeal discomfort
Laryngeal pain
Nasal discharge discolouration
Nasal discomfort
Nasal obstruction
Oropharyngeal blistering
Oropharyngeal discolouration
Oropharyngeal discomfort
Oropharyngeal pain
Paranasal sinus discomfort
Rhinalgia
Rhinorrhoea
Sinus headache
Sinus pain

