## Ethical Considerations:

The results of previous studies of zavegepant support the investigation for the acute treatment of migraine, and there is a favorable benefit-risk profile to support the rationale for this study. Taking into account the measures to minimize risk to participants, the potential risks associated with zavegepant are justified by the anticipated benefits that may be afforded to participants for the acute treatment of migraine.

- Participants may experience improvements during the study and will benefit from more intense monitoring and more frequent assessments compared to usual standard of care. Participants may benefit from contributing to the understanding of the potential efficacy for the acute treatment of migraine, such as freedom from pain, freedom from MBS, and freedom from functional disability.

- Based on the experience with zavegepant, the potential risks for zavegepant are primarily associated with IN administration (ie, dysgeusia, throat irritation, nasal congestion, nasal discomfort), and the majority of AEs have been of mild to moderate intensity.
- Participants randomized to placebo arm may not experience the potential efficacy. Rescue medication or prescribed standard of care medication is permitted during this study.
- Participants will be expected to commit time and may experience some discomfort while undergoing study assessments. In addition, participants of childbearing potential must agree to use appropriate contraception methods.

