**Table 1. Study Schedule of Assessment**

Visit Identifier Abbreviations used in this table may be found in Appendix 8 .	Screen	Treatment Phase			EOT	F/U	Early Discont	Notes
	3-28 days	Day 1 Baseline Visit (Randomization)	Migraine Headache of Moderate or Severe Intensity Before Study Intervention Administration	Post Study Intervention Administration: 15, 30, 45, 60 and 90 minutes, 2, 3, 4, 6, 8, 24 and 48 hours	Within 7 (+2) days of treatment	28-35 days after treatment		
Nasal inspection	X	X			X		X	Baseline Visit may only occur after all screening procedures are completed and the participant meets all inclusion/exclusion criteria. Every effort should be made to conduct the EOT Visit within the specified window of 7 (+2) days after administration of study intervention. If a participant has NOT treated a migraine attack with study intervention within 45 days after randomization, they are still required to complete the EOT Visit. Follow-Up Visit may occur via telephone contact and must occur 28 to 35 days after administration of study intervention. See Section 4.1 for additional information.
Vital signs	X	X			X		X	The nasal passages and turbinates will be visually inspected with a nasal speculum or otoscope at the Screening, Baseline and EOT Visits to detect evidence of nasal inflammation or edema. See Section 8.3.2 for additional information.
12-Lead ECG	X				X		X	See Section 8.3.3 for additional information.
Contraception check	X	X			X	X	X	See Section 8.3.4 for additional information.
Laboratory Assessments								See Section 5.3.1 and Appendix 4 for additional information.
Hematology	X				X		X	See Section 8.3.5 and Appendix 2 for additional information.
Blood chemistry (inc. eGFR)	X				X		X	
Urinalysis	X				X		X	
Urine drug screen for drugs of abuse	X				X		X	
Liver Function Tests (LFTs)	X				X		X	
FSH, if applicable, to determine WOCBP status	X							
HbA1c	X							
Pregnancy test (only for WOCBP)	X (Serum)	X (Urine)			X (Serum)		X (Serum)	A serum pregnancy test will be collected at the Screening and EOT Visits. Confirmatory urine pregnancy test will be completed on site at Baseline Visit and any subsequent visits for confirmation at the investigator's discretion.
Study Intervention and Other Treatments								See Section 6 for additional information.

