### **2.2.2.3. Clinical Safety**

In clinical studies, approximately 2700 participants have been administered zavegepant IN, and approximately 606 participants have been administered oral zavegepant. Administration of zavegepant was well tolerated at 5 mg, 10 mg, and 20 mg as a single IN spray in 1185 adult participants with migraine (BHV3500-201). A similar safety profile was observed in the 629 adult participants administered a single dose of zavegepant 10 mg IN for the acute treatment of migraine (BHV3500-301).

Zavegepant 10 mg IN was well tolerated in a completed long-term safety study (up to 8 doses per month) in 603 adult participants with migraine for up to 52 weeks (BHV3500-202). The most frequently occurring adverse events in clinical studies to date have been associated primarily with intranasal administration (ie, dysgeusia, throat irritation, nasal congestion, nasal discomfort), as well as nausea and back pain, and the majority have been of mild to moderate intensity.

BHV3500-106 was a Phase 1, daily dosing, open-label, safety study of oral zavegepant 100 mg QD in healthy participants. The dose selected for this daily dosing study was based on achieving exposures of zavegepant similar to that for the 10 mg once daily dose administered by the intranasal route. In this study, oral zavegepant 100 mg once daily for up to 8 weeks in healthy participants was well tolerated and demonstrated a favorable safety profile. Through demonstration of clinically relevant sustained systemic exposure after oral administration of zavegepant, the results of this study support the safety conclusions and the overall benefit-risk assessment for the intranasal route of administration.

Refer to the IB for more details on the clinical safety of zavegepant.

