### 2.3.1. Risk Assessment

Potential Risk of Clinical Significance	Summary of Data/Rationale for Risk	Mitigation Strategy
Study Intervention: Zavegepant		
AEs associated with IN administration, such as dysgeusia, throat irritation, nasal congestion and nasal discomfort.	The potential risks are based on AEs reported in studies of zavegepant IN administration, and the majority have been of mild to moderate intensity.	Eligibility criteria have been selected to ensure that only appropriate participants are included in the study (see Section 5). Nasal inspection will be conducted on Screening Visit, Baseline Visit and EOT Visit per the SoA. AEs and clinical laboratory results will be monitored on an ongoing basis.
Use of a placebo arm.	Participants randomized to placebo arm may not experience freedom from pain and freedom from MBS efficacy, as well as freedom from functional disability.	Rescue medication or prescribed standard of care medication is permitted during this study as specified in Section 6.9.2.

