### Local Irritation AEs

Local irritation AE PTs include any of the following:

- “Administrative site reactions NEC” high level term (HLT): PTs in [Table 5 \(Appendix 3.2\)](#) based on clinical review. NEC=not elsewhere classified.
- “Upper respiratory tract signs and symptoms” HLT: PTs in [Table 6 \(Appendix 3.2\)](#) based on clinical review.
- Dysgeusia.

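### The grouped local irritation AE definition leaves out nasal congestion, one of the four intranasal reactions the protocol names

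*SAP*

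**What the plan says.** **Protocol.** The risk table in Section 2.3.1 has one row specific to the drug: "AEs associated with IN administration, such as dysgeusia, throat irritation, nasal congestion and nasal discomfort". The other row concerns the use of a placebo arm. The same four reactions, "dysgeusia, throat irritation, nasal congestion, nasal discomfort", appear in Section 2.2.2.3, where they lead the AEs seen most often so far (nausea and back pain follow). They also appear in the synopsis under Ethical Considerations and in Section 2.3.2. Section 8.4.8 makes local irritation an AE of special interest and bases the term mapping on a core SAP that is not among the documents.

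**SAP.** Section 3.2.2 lists local irritation AEs as one component of the secondary safety endpoint. Section 6.6.1.1 gives them a row in the AE overview, and Section 6.6.1.3 gives them their own table. Section 6.6.1.3 builds the definition from three parts:

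- the PTs in Table 5, attributed to the "Administrative site reactions NEC" HLT;
- the PTs in Table 6, from the "Upper Respiratory Tract Signs and Symptoms" HLT;
- dysgeusia, as a separate single term.

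Table 5 itself is titled with a different HLT, "Application and Instillation Site Reactions".

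**The concern.** The grouped row is where a reader will look for the overall rate of local reactions to the spray. It should therefore cover at least the reactions the protocol itself presents as the product's known risk, and by exact term it covers three of the four. Participants with several reactions appear in several PT rows, so the number with any local reaction cannot be rebuilt from the PT tables. If the grouped row omits a named reaction, nothing else in the planned output supplies that participant-level count.

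**Working it through.** **Step 1: size of the definition.** Table 5 has 18 PTs, Table 6 has 26 across its two pages, and dysgeusia adds 1: 18 + 26 + 1 = 45 terms.

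**Step 2: match the four named reactions to the list by exact term.**

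| Reaction named in the protocol | In the SAP definition? | Where |
|---|---|---|
| Dysgeusia | Yes | Section 6.6.1.3, single term |
| Throat irritation | Yes | Table 6 |
| Nasal discomfort | Yes | Table 6 |
| Nasal congestion | No | In neither table nor the section text |

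Three of four are captured. The nearest listed terms are 'Nasal obstruction' and 'Upper respiratory tract congestion'. Selection is by PT, so neither picks up an event coded as nasal congestion.

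**Step 3: is the gap only lost text?** Table 6 is in alphabetical order throughout. Nasal congestion would stand just before 'Nasal discharge discolouration'. The page break falls elsewhere, between 'Sinus pain' and 'Sneezing'. The omission does not look like a reading error.

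**Step 4: possible size.** Protocol Section 9.5 expects about 90% of 700 per arm to be evaluable: 0.90 × 700 = 630. That figure is for efficacy and stands in here for the number treated. No nasal congestion rate is given for either arm, so q, the share of an arm whose only local event is nasal congestion, is an assumption. Participants missed = q × 630:

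- q = 0: 0
- q = 0.5%: 3.15, about 3
- q = 1%: 6.3, about 6
- q = 2%: 12.6, about 13
- q = 5%: 31.5, about 32

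The arm's grouped rate falls by q, so at q = 1% it falls by 1 percentage point. The lower end really is zero: if every participant with nasal congestion also has a listed term, the count does not change.

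**Step 5: effect on the comparison of arms.** Write q_z and q_p for the shares in the zavegepant and placebo arms. The tabulated difference equals the difference under the four-reaction definition minus (q_z − q_p). It is understated if q_z exceeds q_p, unchanged if they are equal, and overstated if q_p is larger. The documents give neither share.

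**The case against.** **The event is reported elsewhere.** Nasal congestion will appear by SOC and PT, by severity and by arm, in the on-treatment and follow-up TEAE tables (SAP Sections 6.6.1.2.2 and 6.6.1.2.3). Moderate or severe cases also count in another component of the same secondary endpoint. The grouped row is a frequency tabulation outside the testing hierarchy of SAP Section 5.1. All of this stands. It limits the consequence to one grouped row and its table, and rules out any effect on efficacy or confirmatory conclusions.

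**The definition can still change.** SAP Section 6.6.1.3 allows minor updates before database lock, and the unseen core SAP may treat the term differently. That provides a route for the correction but does not put the term into the current text.

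**The term may belong to another HLT.** The documents do not show this. Dysgeusia already stands in the definition outside both HLT lists, so a single-term addition has a precedent.

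**Stronger readings that a reader might infer, and that the documents do not support:**

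- *That the list misses what the nasal inspection looks for.* The schedule of activities says the inspection is done "to detect evidence of nasal inflammation or edema". Table 5 contains 'Administration site inflammation', 'Administration site oedema', 'Administration site swelling' and 'Administration site ulcer', and Table 6 contains 'Upper respiratory tract inflammation'. Nose-specific wording is absent, but whether a nasal finding would be coded to one of these terms depends on coding conventions that are not in the documents.
- *That application-site and instillation-site terms are wrongly excluded.* The only basis is the Table 5 title. All 18 PTs begin with 'Administration site', which fits the kind of HLT named in Section 6.6.1.3. Nothing shows that the other terms were intended. The mismatch is clerical.
- *That the loss falls mainly on zavegepant, so that the between-arm difference is understated.* No rate by arm is given, and placebo is also an intranasal spray.

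**Conclusion.** The point holds in a limited form. The local irritation definition captures three of the four intranasal reactions that the protocol names, and a participant with only nasal congestion falls outside it. The grouped rate can therefore be understated, by anywhere from none to about 32 participants per arm under the assumed range of 0 to 5%. That range is illustrative, and neither the true size nor the direction of any effect on the arm comparison can be determined.

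The conclusion assumes that nasal congestion is coded to a term of its own. An event coded instead to 'Nasal obstruction', for example, would be counted.

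This should be fixed, because the gap is in a named secondary safety component and the remedy is cheap. It is not critical, because the row is descriptive and the event is reported by PT elsewhere.

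**What to change.** Before database lock and unblinding, add 'Nasal congestion' to the local irritation definition in SAP Section 6.6.1.3 as a single term, in the same way as dysgeusia. The definition then holds 45 + 1 = 46 terms and covers all four named reactions. If the omission is deliberate, state the reason there instead. In the same edit, make the HLT name in Section 6.6.1.3 and the title of Table 5 agree.

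The cost is one added term in the SAP and in the analysis program, plus one corrected label. The only downside is that the reported local irritation rate may be slightly higher. Timing matters: the same change made after unblinding would look driven by the data.

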**Table 6. PTs in “Upper Respiratory Tract Signs and Symptoms” HLT from Clinical Review**

PTs
Sneezing Throat clearing Throat irritation Upper respiratory tract congestion Upper respiratory tract inflammation Upper respiratory tract irritation Upper-airway cough syndrome

090177e1a3a7d3d9\Approved\Approved On: 30-May-2025 05:10 (GMT)

#### **Appendix 4. Laboratory Test Toxicity Grades**

Laboratory test toxicity grades are assigned using CTCAE or DAIDS criteria as specified in [Table 7](#).

If a value falls into  $> 1$  toxicity grade category, then the highest toxicity grade is chosen.

If fasting status is yes, then fasting toxicity grades are used. Otherwise, nonfasting toxicity grades are used.

090177e1a3a7d3d9\Approved\Approved On: 30-May-2025 05:10 (GMT)

**Table 7. Laboratory Test Toxicity Grades**

Test Name	Grade				
	0	1	2	3	4
Hematology					
Eosinophils *	≤ ULN or ≤ baseline	{> ULN and > baseline} or {> ULN and baseline missing}			
Hemoglobin	≥ LLN	≥ 10.0 to < LLN g/dL; ≥ 6.2 to < LLN mmol/L; ≥ 100 to < LLN g/L	≥ 8.0 to < 10.0 g/dL; ≥ 4.9 to < 6.2 mmol/L; ≥ 80 to < 100 g/L	< 8.0 g/dL; < 4.9 mmol/L; < 80 g/L	
Lymphocytes, high	≤ 4,000/mm 		> 4,000 to ≤ 20,000/mm 	> 20,000/mm 	
Lymphocytes, low	≥ LLN	≥ 800 to < LLN/mm  ; ≥ 0.8 to < LLN x 10  /L	≥ 500 to < 800/mm  ; ≥ 0.5 to < 0.8 x 10  /L	≥ 200 to < 500/mm  ; ≥ 0.2 to < 0.5 x 10  /L	< 200/mm  ; < 0.2 x 10  /L
Neutrophils	≥ LLN	≥ 1,500 to < LLN/mm  ; ≥ 1.5 to < LLN x 10  /L	≥ 1,000 to < 1,500/mm  ; ≥ 1.0 to < 1.5 x 10  /L	≥ 500 to < 1,000/mm  ; ≥ 0.5 to < 1.0 x 10  /L	< 500/mm  ; < 0.5 x 10  /L
Platelets	≥ LLN	≥ 75,000 to < LLN/mm  ; ≥ 75.0 to < LLN x 10  /L	≥ 50,000 to < 75,000/mm  ; ≥ 50.0 to < 75.0 x 10  /L	≥ 25,000 to < 50,000/mm  ; ≥ 25.0 to < 50.0 x 10  /L	< 25,000/mm  ; < 25.0 x 10  /L
White blood cell count	≥ LLN	≥ 3000 to < LLN/mm  ; ≥ 3.0 to < LLN x 10  /L	≥ 2000 to < 3000/mm  ; ≥ 2.0 to < 3.0 x 10  /L	≥ 1000 to < 2000/mm  ; ≥ 1.0 to < 2.0 x 10  /L	< 1000/mm  ; < 1.0 x 10  /L
Serum chemistry					
Albumin	≥ LLN	≥ 3 to < LLN g/dL; ≥ 30 to < LLN g/L	≥ 2 to < 3 g/dL; ≥ 20 to < 30 g/L	< 2 g/dL; < 20 g/L	
ALP *	≤ ULN if baseline ≤ ULN or missing; < 2.0 x baseline	> ULN to ≤ 2.5 x ULN if baseline ≤ ULN or missing;	> 2.5 to ≤ 5.0 x ULN if baseline ≤ ULN or missing;	> 5.0 to ≤ 20.0 x ULN if baseline ≤ ULN or missing;	> 20.0 x ULN if baseline ≤ ULN or missing; > 20.0 x baseline if

Test Name	Grade				
	0	1	2	3	4
ALT *	if baseline > ULN  ≤ ULN if baseline ≤ ULN or missing; < 1.5 x baseline if baseline > ULN	≥ 2.0 to ≤ 2.5 x baseline if baseline > ULN  > ULN to ≤ 3.0 x ULN if baseline ≤ ULN or missing; ≥ 1.5 to ≤ 3.0 x baseline if baseline > ULN	> 2.5 to ≤ 5.0 x baseline if baseline > ULN  > 3.0 to ≤ 5.0 x ULN if baseline ≤ ULN or missing; ≥ 3.0 to ≤ 5.0 x baseline if baseline > ULN	> 5.0 to ≤ 20.0 x baseline if baseline > ULN  > 5.0 to ≤ 20.0 x ULN if baseline ≤ ULN or missing; ≥ 5.0 to ≤ 20.0 x baseline if baseline > ULN	baseline > ULN  > 20.0 x ULN if baseline ≤ ULN or missing; > 20.0 x baseline if baseline > ULN
AST *	≤ ULN if baseline ≤ ULN or missing; < 1.5 x baseline if baseline > ULN	> ULN to ≤ 3.0 x ULN if baseline ≤ ULN or missing; ≥ 1.5 to ≤ 3.0 x baseline if baseline > ULN	> 3.0 to ≤ 5.0 x ULN if baseline ≤ ULN or missing; ≥ 3.0 to ≤ 5.0 x baseline if baseline > ULN	> 5.0 to ≤ 20.0 x ULN if baseline ≤ ULN or missing; ≥ 5.0 to ≤ 20.0 x baseline if baseline > ULN	> 20.0 x ULN if baseline ≤ ULN or missing; > 20.0 x baseline if baseline > ULN
Bicarbonate	≥ LLN	< LLN			
Bilirubin (total) *	≤ ULN if baseline ≤ ULN or missing; ≤ 1.0 x baseline if baseline > ULN	> ULN to ≤ 1.5 x ULN if baseline ≤ ULN or missing; > 1.0 to ≤ 1.5 x baseline if baseline > ULN	> 1.5 to ≤ 3.0 x ULN if baseline ≤ ULN or missing; ≥ 1.5 to ≤ 3.0 x baseline if baseline > ULN	> 3.0 to ≤ 10.0 x ULN if baseline ≤ ULN or missing; ≥ 3.0 to ≤ 10.0 x baseline if baseline > ULN	> 10.0 x ULN if baseline ≤ ULN or missing; > 10.0 x baseline if baseline > ULN
Calcium, high	≤ ULN	> ULN to ≤ 11.5 mg/dL; > ULN to ≤ 2.9 mmol/L	> 11.5 to ≤ 12.5 mg/dL; > 2.9 to ≤ 3.1 mmol/L	> 12.5 to ≤ 13.5 mg/dL; > 3.1 to ≤ 3.4 mmol/L	> 13.5 mg/dL; > 3.4 mmol/L
Calcium, low	≥ LLN	≥ 8.0 to < LLN mg/dL; ≥ 2.0 to < LLN mmol/L	≥ 7.0 to < 8.0 mg/dL; ≥ 1.75 to < 2.0 mmol/L	≥ 6.0 to < 7.0 mg/dL; ≥ 1.5 to < 1.75 mmol/L	< 6.0 mg/dL; < 1.5 mmol/L
Cholesterol (total)	≤ ULN	> ULN to ≤ 300 mg/dL; > ULN to ≤ 7.75 mmol/L	> 300 to ≤ 400 mg/dL; > 7.75 to ≤ 10.34 mmol/L	> 400 to ≤ 500 mg/dL; > 10.34 to ≤ 12.92 mmol/L	> 500 mg/dL; > 12.92 mmol/L
CK #	≤ ULN	> ULN to ≤ 2.5 x ULN	> 2.5 to ≤ 5 x ULN	> 5 to 10 x ULN	> 10 x ULN
Creatinine	≤ ULN	> ULN to ≤ 1.5 x ULN	{> 1.5 to ≤ 3.0 x ULN} or {> 1.5 to ≤ 3.0 x baseline}	{> 3.0 to ≤ 6.0 x ULN} or {> 3.0 x baseline}	> 6.0 x ULN

Test Name	Grade				
	0	1	2	3	4
eGFR MDRD	≥ LLN	≥ 60 to < LLN mL/min/1.73 m 	≥ 30 to < 60 mL/min/1.73 m 	≥ 15 to < 30 mL/min/1.73 m 	< 15 mL/min/1.73 m 
Glucose, high, fasting @*	< 110 mg/dL; < 6.11 mmol/L	≥ 110 to ≤ 125 mg/dL; ≥ 6.11 to < 6.95 mmol/L	> 125 to ≤ 250 mg/dL; ≥ 6.95 to < 13.89 mmol/L	> 250 to ≤ 500 mg/dL; ≥ 13.89 to < 27.75 mmol/L	> 500 mg/dL; ≥ 27.75 mmol/L
Glucose, high, nonfasting @*	< 116 mg/dL; < 6.44 mmol/L	≥ 116 to ≤ 160 mg/dL; ≥ 6.44 to < 8.89 mmol/L	> 160 to ≤ 250 mg/dL; ≥ 8.89 to < 13.89 mmol/L	> 250 to ≤ 500 mg/dL; ≥ 13.89 to < 27.75 mmol/L	> 500 mg/dL; ≥ 27.75 mmol/L
Glucose, low @	> 64 mg/dL; ≥ 3.55 mmol/L	≥ 55 to ≤ 64 mg/dL; ≥ 3.05 to < 3.55 mmol/L	≥ 40 to < 55 mg/dL; ≥ 2.22 to < 3.05 mmol/L	≥ 30 to < 40 mg/dL; ≥ 1.67 to < 2.22 mmol/L	< 30 mg/dL; < 1.67 mmol/L
Lactate dehydrogenase	≤ ULN	> ULN			
LDL cholesterol, age ≥ 18 years @	< 130 mg/dL; < 3.37 mmol/L	≥ 130 to < 160 mg/dL; ≥ 3.37 to < 4.12 mmol/L	≥ 160 to < 190 mg/dL; ≥ 4.12 to < 4.90 mmol/L	≥ 190 mg/dL; ≥ 4.90 mmol/L	
LDL cholesterol, age > 2 to < 18 years @*	< 110 mg/dL; < 2.85 mmol/L	≥ 110 to < 130 mg/dL; ≥ 2.85 to < 3.37 mmol/L	≥ 130 to < 190 mg/dL; ≥ 3.37 to < 4.90 mmol/L	≥ 190 mg/dL; ≥ 4.90 mmol/L	
Potassium, high	≤ ULN	> ULN to ≤ 5.5 mmol/L	> 5.5 to ≤ 6.0 mmol/L	> 6.0 to ≤ 7.0 mmol/L	> 7.0 mmol/L
Potassium, low	≥ LLN	≥ 3.0 to < LLN mmol/L		≥ 2.5 to < 3.0 mmol/L	< 2.5 mmol/L
Sodium, high	≤ ULN	> ULN to ≤ 150 mmol/L	> 150 to ≤ 155 mmol/L	> 155 to ≤ 160 mmol/L	> 160 mmol/L
Sodium, low	≥ LLN	≥ 130 to < LLN mmol/L	≥ 125 to < 130 mmol/L	≥ 120 to < 125 mmol/L	< 120 mmol/L
Triglycerides	< 150 mg/dL; < 1.71 mmol/L	≥ 150 to ≤ 300 mg/dL; ≥ 1.71 to ≤ 3.42 mmol/L	> 300 to ≤ 500 mg/dL; ≥ 3.42 to ≤ 5.7 mmol/L	> 500 to ≤ 1000 mg/dL; ≥ 5.7 to ≤ 11.4 mmol/L	> 1000 mg/dL; ≥ 11.4 mmol/L
Uric acid (urate) @	< 7.5 mg/dL; < 0.45 mmol/L	≥ 7.5 to < 10.0 mg/dL; ≥ 0.45 to < 0.59 mmol/L	≥ 10.0 to < 12.0 mg/dL; ≥ 0.59 to < 0.71 mmol/L	≥ 12.0 to < 15.0 mg/dL; ≥ 0.71 to < 0.89 mmol/L	≥ 15.0 mg/dL; ≥ 0.89 mmol/L

Test Name	Grade				
	0	1	2	3	4
Urinalysis					
Urine glucose @*	Negative; ≤ 180 mg/dL	Trace or 1+; > 180 to ≤ 250 mg/dL	2+; > 250 to ≤ 500 mg/dL	3+ or higher; > 500 mg/dL	
Urine protein @*	Negative; < 10 mg/dL	Trace or 1+; ≥ 10 to < 100 mg/dL	2+; ≥ 100 to < 300 mg/dL	3+ or higher; ≥ 300 mg/dL	

@ Graded using DAIDS criteria. All other laboratory tests are graded using CTCAE criteria.

\* Modified toxicity grade criteria to correct typos, handle missing baseline, or include additional selection criteria.

For urine glucose, 180 mg/dL is considered the commonly accepted "normal" threshold.

For urine protein, < 10 mg/dL is considered the commonly accepted "normal" threshold.

